11.4.3. Secondary Immunogenicity Data

Immunogenicity data summaries and analysis will be presented for both the ITT and PP populations. Pre-second vaccination, Study Groups 1, 2, 3 will be analyzed jointly as one study group as all three study groups received the same vaccine at Day 1.

Seroconversion for anti-EBOV GP ELISA (defined as EBOV GP ELISA titer > 50 if baseline (Day 1) titer ≤ 50 or fold rise of > 4 -fold as compared to baseline if the baseline titer > 50), will be summarized for each post-vaccination study visit day (Day 8, 15, 22, 29 and 36) and study

group using percentages and exact two-sided 95% CIs. Per-visit seroconversion percentages and CIs will be visualized across study visit days using time trend plots.

Anti-EBOV GP ELISA titer at Day 1, 8, 15, 22, 29 and 36 will be summarized by calculating the geometric mean (GMT) titer and corresponding 95% CIs for each study group and day by transforming individual titer results to a logarithmic scale, assuming asymptotic normality conditions were satisfied on this scale, computing the mean and 95% CI then converting back to the original scale. Per-visit GMTs and CIs will be visualized across study visit days using time trend plots.

Change in Anti-EBOV GP ELISA titer at Day 8, 15, 22, 29 and 36 compared to baseline (Day 1) will be summarized by calculating the geometric mean fold rise (GMFR) and corresponding 95% CIs for each study group and day by dividing the post-vaccination titer for each subject by the respective pre-vaccination titer, transforming ratios to a logarithmic scale, assuming asymptotic normality conditions were satisfied on this scale, computing the mean and 95% CI then converting back to the original scale. Per-visit GMFR and CIs will be visualized across post-vaccination study visit days using time trend plots.

11.4.4. Exploratory Data Analyses

Pre-second vaccination, Study Groups 1, 2, 3 will be analyzed jointly as one study group as all three study groups received the same vaccine at Day 1.

GMT of neutralizing antibodies to EBOV GP at Day 8 and 15 and GMFR in titer on Day 8 and 15 compared to baseline (Day 1) and associated 95% CIs will be calculated and summarized as described in [Section 11.4.3](#). Significant differences in neutralizing antibodies to EBOV GP or Anti-EBOV GP ELISA titer between study groups for each post-second vaccination time points will be evaluated using a two-sided Welch's T-test using an individual alpha of 0.05. Differences in Anti-EBOV GP ELISA-based seroconversion at post-second vaccination time points will be assessed using a two-sided Fishers' exact test using an individual alpha of 0.05.

Baseline fold changes for³⁵ percentage of killed cells³⁶ percentage of activated CD4+ and CD8+ T cells³⁷, cytokine concentrations³⁸, percentage of EBOV GP-specific cytokine secreting CD4+ and CD8+ T cells expression one, two, or multiple makers³⁹, percentage of EBOV GP-specific CD4+ and CD8+ T cells⁴⁰, percentage of ChAd3-specific cytokine secreting CD4+ and CD8+ T cells⁴¹, percentage of CD19+CD27+CD38+ plasmablasts will be summarized using minimum, Q1, median, Q3, maximum, and 95% CI of the median. The 95% CI of the median fold change from baseline will be determined by using the bootstrap method and visualized using time trend plots. To identify features that show a differential response from baseline, a two-sided Wilcoxon signed-rank test will be carried out for each study group using an individual alpha of 0.05. Significant differences in fold changes between study groups for post-second vaccination time

points will be evaluated using a two-sided Wilcoxon rank-sum test using an individual alpha of 0.05.

For the transcriptomics exploratory analysis, RNA-Seq data will be pre-processed by removing adapters and low-quality reads and mapping sequences to the latest human reference genome using splice-aware alignment software such as *HISAT2*³⁵. Gene expression quantification will be carried out by using the *Subread* software³⁶ using the latest Ensembl³⁷ gene model annotations as a reference. Systematic differences in sequence coverage between samples will be accounted for using the TMM method³⁸ as implemented in the *edgeR*³⁹ R package. Principal component analysis, non-metric multidimensional scaling, and hierarchical clustering analysis will be used to identify potential global outliers and systematic batch effect. Negative binomial models as implemented in *edgeR*³⁹ will be used to identify genes for each study group and post-vaccination day that were differentially expressed (DE) compared to pre-vaccination as well as genes that were DE between study groups. If the analysis reveals a systematic batch effect that is not associated with study group, it will be accounted for by adding a batch blocking factor as part of the negative binomial models. To control for testing multiple genes, the false-discovery rate (FDR) based on the Benjamini-Hochberg procedure⁴⁰ as implemented in the *p.adjust* R function will be applied. Genes with a FDR-value < 0.05 and a fold change of greater or equal to 1.5-fold (up or down regulation) will be deemed to be significantly DE. Depending on observed treatment effects, this fold change cut off may be revised. The *pvclust*⁴¹ R package will be applied to identify co-expressed DE gene clusters and cluster time trends will be visualized. Pathway enrichment analysis based on the latest MSigDB⁴² and KEGG⁴³ databases as well as Blood Transcription Modules⁴⁴ accounting for gene length bias will be carried out using the implementation provided by the *goseq*⁴⁵ R package. Pathway maps color-coded by treatment effect will be provided for significantly enriched KEGG pathways. Regularized canonical correlation analysis and regularized linear regression analysis as implemented in the mixOmics⁴⁶ and *glmnet*⁴⁷ R packages, respectively will be utilized to identify gene expression changes that are associated with adaptive humoral and/or cellular immune response endpoints. In both cases, cross-validation will be used to select optimal models.

Please see the separate document “**Statistical Analysis Plan**” for additional information on exploratory endpoint analyses.

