3.2.3. Exploratory

- GMT of neutralizing antibodies to EBOV GP at Day 1, 8 and 15 as measured by EBOV GP pseudovirion neutralization assay.
- GMFR in titer on Day 8 and 15 compared to baseline (Day 1) as measured by EBOV GP pseudovirion neutralization assay.
- Change in the percentage of killed cells as measured by ADCC on Day 8, 15, 22, 29, and 36 compared to baseline (Day 1).
- Change in percentage of activated CD4+ and CD8+ T cells for each cell subpopulation on Day 8 and 15 compared to baseline (Day 1) as measured by flow cytometry.
- Change in cytokine concentration and CRP on Day 2, 3, 4, 6, 8, 9 and 15 compared to baseline (Day 1) as measured by Luminex assay and clinical laboratory CRP assay, respectively.
- Change in percentage of EBOV GP-specific cytokine secreting CD4+ and CD8+ T cells on Day 8, 15, 22, and 36 compared to baseline (Day 1) as measured by intracellular cytokine staining (ICS).
- Change in percentage of EBOV GP-specific CD4+ and CD8+ T cells on Day 8 and 15 as compared to baseline (Day 1) measured by tetramer staining for predominant human leukocyte antigen (HLA) types.
- Change in percentage of ChAd3-specific cytokine secreting CD4+ and CD8+ T cells on Day 8, 15, 22 and 36 compared to baseline (Day 1) as measured by ICS.

- Change in percentage of CD19+CD27+CD38+ plasmablasts on Day 8 and 15 compared to baseline (Day 1) as measured by flow cytometry.
- Change in B-cell repertoire (BCR) on Day 8 and 15 as compared to baseline (Day 1) from sorted CD19+ CD27+ CD38+ plasmablasts as measured by immunoglobulin heavy chain sequencing.
- Characterization of antigen-specific BCR as measured by yeast display on day 36.
- Change in gene expression in PBMCs on Day 2, 3, 4, 6, 8, 9, and 15 compared to baseline (Day 1) as measured by RNA-Seq.
- Identification of gene expression changes on Day 2, 3, 4, 6, 8, 9, and 15 associated with each subject's peak change in percentage of EBOV GP-specific cytokine secreting CD4+ and CD8+ T cells across Day 15, 22, and 36.
- Identification of gene expression changes on Day 2, 3, 4, 6, 8, 9, and 15 associated with each subject's peak anti-EBOV GP ELISA titer across Day 15, 22, 29, and 36.
- Identification of gene expression changes on Day 2, 3, 4, 6, 8, 9, and 15 associated with each subject's EBOV neutralizing antibody titer at Day 15.

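### The within-group signed-rank test in Protocol 11.4.4 has no stated scale; read naturally as a test of raw fold change, it favours increases

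*Protocol*

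**What the plan says.** The relevant paragraph of Protocol 11.4.4 covers ADCC killing, activated T cells, cytokine concentrations, antigen- and vector-specific T cells, and plasmablasts. It summarises each feature's fold change from baseline by quantiles, with "The 95% CI of the median fold change from baseline will be determined by using the bootstrap method". It then plans the test, at an individual alpha of 0.05: "To identify features that show a differential response from baseline, a two-sided Wilcoxon signed-rank test will be carried out for each study group". The next sentence, on the rank-sum comparison, names its variable: "Significant differences in fold changes between study groups for post-second vaccination time" points. The signed-rank sentence names none.

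Protocol 11.4.3 handles antibody ratios differently. For the ELISA fold rise it prescribes "transforming ratios to a logarithmic scale, assuming asymptotic normality conditions were satisfied on this scale". Protocol 11.4.4 carries that method over to the neutralization titres only.

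The outcome definitions in Protocol 3.2.3 speak of change without saying ratio or difference, for example "Change in the percentage of killed cells as measured by ADCC on Day 8, 15, 22, 29, and 36 compared to baseline (Day 1").

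Protocol 11.4.4 also analyses the three groups jointly before the second vaccination, which means about 60 subjects; afterwards there are 20 per arm. SAP 6.1 includes Day 8 in the joint period. SAP 1, 4.5.3 and 10 send these endpoints to an addendum that is not among the documents available.

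**The concern.** Fold change is the variable named both before and after the signed-rank sentence, and no log step is mentioned. An analyst following the text literally would test fold change minus 1.

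The signed-rank test is not invariant to a log transform. Its null hypothesis is symmetry about the null value. A ratio with no true change may be symmetric on the log scale, but on the raw scale a doubling counts as +1 and a halving as -0.5. Rises therefore take the larger ranks, and the test responds to skewness as well as to change.

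The lists of responding features would then lean towards increases, and real decreases would be missed. A feature could also be called significant while the bootstrap interval for its median fold change includes 1. The bias grows with sample size, so it is greatest in the pooled pre-boost analysis of early cytokines and CRP. That analysis serves the first of the two major objectives in Protocol 2.2, early innate responses.

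**Working it through.** **Stated figure.** The only one is the two-sided individual alpha of 0.05. It is a design setting, so there is no derived figure to reproduce. The question is whether the test keeps it.

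**Hand example.** Take four subjects with fold changes 2, 1/2, 3 and 1/3, which balance exactly on the log scale.
- Raw fold change minus 1: +1, -0.5, +2, -0.667. Ranks of the absolute values: 3, 1, 4, 2. Positive rank sum = 3 + 4 = 7, against an expected 10/2 = 5.
- Log fold change: the absolute values tie in pairs, with ranks 1.5, 1.5, 3.5, 3.5. Positive rank sum = 1.5 + 3.5 = 5, as expected.

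**Simulation inputs.** n = 20 per arm and 60 pooled (Protocol 5.4.5 and 11.4.4); two-sided alpha 0.05 (Protocol 11.4.4). Assumption: ln(fold change) ~ N(0, s) under no change, so the median fold change is 1. The documents do not give s, so a range is shown. There were 4,000 data sets per cell, with Monte Carlo standard error at 5% of sqrt(0.05 × 0.95 / 4000) = 0.34 points.

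**Rejection rate with no change**

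| n | s | Raw fold change: total | Raw: up / down | Log fold change: total |
|---|---|---|---|---|
| 20 | 0.2 | 5.5% | 3.7 / 1.8 | 5.1% |
| 20 | 0.3 | 5.7% | 4.0 / 1.7 | 4.8% |
| 20 | 0.5 | 6.9% | 6.0 / 0.9 | 4.8% |
| 20 | 0.7 | 8.4% | 7.8 / 0.6 | 4.8% |
| 20 | 1.0 | 10.4% | 10.1 / 0.4 | 4.4% |
| 60 | 0.2 | 6.1% | 5.3 / 0.7 | 4.7% |
| 60 | 0.3 | 7.9% | 7.4 / 0.5 | 4.8% |
| 60 | 0.5 | 12.9% | 12.6 / 0.4 | 5.4% |
| 60 | 0.7 | 18.7% | 18.6 / 0.1 | 4.7% |
| 60 | 1.0 | 29.2% | 29.1 / 0.1 | 5.1% |

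Separate runs put the last raw cell between 28% and 30%.

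**Power for a true 25% decrease, raw v log.** n=20: 46% v 66% (s=0.5) and 19% v 38% (s=0.7). n=60: 46% v 86% (s=0.7) and 12% v 58% (s=1.0).

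**Power for a 1.5-fold rise v a 1.5-fold fall, n=20, s=0.7.** Raw: 83% v 41%. Log: 66% v 67%.

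**Alternative reading: raw paired differences, post minus pre.**
- Pre and post exchangeable: size 4.3 to 5.3%, evenly split between directions. Power for the 25% decrease is 1 to 7 points below log: 34% v 38% (n=20, s=0.7), 80% v 86% (n=60, s=0.7), 52% v 58% (n=60, s=1.0).
- Multiplicative noise added after baseline (between-subject log-SD of 1 assumed): size at n=60 is 11.3% at s=0.7 and 17.2% at s=1.0, again nearly all upward.

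**Where n=60 applies.** Protocol 3.2.3 lists cytokines and CRP on Days 2, 3, 4, 6, 8, 9 and 15. Days 2, 3, 4, 6 and 8 precede the boost, so five of seven days are pooled. For the other features the first post-baseline visit is Day 8, so only that day is pooled.

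**The case against.** The strongest objection is that the text never says the fold changes are untransformed. A signed-rank test is a paired test, and comparing post with pre values is an ordinary reading of it. Protocol 3.2.3 commits to neither ratio nor difference, and the detail is deferred to an addendum that may already specify logs. This stands: a reader might infer that the plan prescribes a test on raw fold changes, or that the addendum leaves the matter open, but the documents support neither. What they support is that the scale is unstated and that raw fold change is its most natural reading.

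Falling back on paired differences does not fully answer the point. That version keeps its level when pre and post are exchangeable, but not when multiplicative noise enters after baseline, and the documents do not establish which applies.

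The size also depends on an SD that is not given. At s of 0.2 or less the effect is slight, and lognormality is itself an assumption, for percentages as well as concentrations. Both limits stand.

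Finally, Protocol 11.1 describes a hypothesis-generating study with no formal null hypothesis, and medians with bootstrap intervals are reported beside the tests. That limits the consequences. It does not justify leaving the scale open, because the individual alpha is the only error control stated for these tests; SAP 6.8 reserves false-discovery control for high-dimensional -omics endpoints.

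**Conclusion.** The point holds as an unspecified test scale whose natural reading is a poor choice. Under lognormal values, raw fold change gives about 6 to 8% false positives at n=60 when s is 0.2 to 0.3, rising to about 13%, 19% and 29% at 0.5, 0.7 and 1.0. At n=20 the range is about 6 to 10% for s from 0.3 to 1.0. The loss for decreases can be large: at n=60 and s=0.7, power for a 25% fall drops from 86% to 46%.

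A reader might infer that the whole systems-biology output is affected. It is not. Gene expression uses negative binomial models in edgeR with false-discovery control, and the between-arm rank-sum test is unchanged by a log transform. The median fold changes and their intervals are also untouched, and no primary or secondary conclusion rests on these p-values. This is a cheap improvement to an exploratory analysis.

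**What to change.** In Protocol 11.4.4 and the SAP addendum, state that the signed-rank test is applied to each subject's log2 fold change from Day 1, against 0. Pre-specify one floor value for zero or undetectable readings, set before ratios are formed; a ratio needs this anyway when the baseline is zero. If the addendum already says so, a cross-reference is enough. Keep the median fold change and its bootstrap interval on the original scale, and leave the rank-sum test as it is.

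The cost is one sentence, with no new data or procedures. The downsides are that a floor must be chosen and that fewer increases will be flagged.

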5.4. Treatment Assignment Procedures

5.4.1. Randomization Procedures

Per International Council for Harmonisation of Technical Requirements for Pharmaceuticals for Human Use (ICH) guideline E6: Good Clinical Practice (GCP), screening records will be kept at the participating VTEU site to document the reason why an individual was screened, but failed trial entry criteria. The reasons why individuals failed screening will be recorded in the Statistical and Data Coordinating Center's AdvantageEDCSM (Electronic Data Capture System).

Once consented and upon entry of demographic data and confirmation of eligibility for this trial, the subjects will be enrolled. Subjects will be randomized 1:1:1 in double-blind fashion to 1 dose of ChAd3-EBO-Z vaccine at Day 1 followed by a booster of placebo, ChAd3-EBO-Z (homologous), or MVA-BN®-Filo (heterologous) at Day 8.

Enrollment of subjects will be done online using the enrollment module of AdvantageEDCSM. The randomization code will be prepared by statisticians at the SDCC and included in the enrollment module for this trial. AdvantageEDCSM will assign each subject to a treatment arm after the demographic and eligibility data have been entered into the system. A designated individual at the participating VTEU site will be provided with a code list for emergency unblinding purposes, which will be kept in a secure place.

Instructions for use of the enrollment module are included in the AdvantageEDCSM User's Guide. Manual back-up randomization procedures and instructions are provided for use in the event that a participating VTEU site temporarily loses access to the Internet or the online enrollment system is unavailable.

Subjects who sign the informed consent form (ICF) and are randomized but do not receive study vaccine may be replaced. Subjects who sign the informed consent form, and are randomized and vaccinated, and subsequently withdraw, or are withdrawn or terminated from this trial, or are lost to follow-up may be replaced.

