5.4.2. Masking Procedures

This is a double-blind clinical trial. Subjects, investigators, study personnel performing any study-related assessments following study vaccine administration, and laboratory personnel performing antibody assays will be blinded to treatment arm assignment (i.e., type of booster). Laboratory personnel performing experimental assays including antibody assays will also be masked to subject ID and study visit.

The randomization scheme will be generated by the SDCC and provided to unblinded study personnel (i.e., research pharmacists performing study vaccination preparations and unblinded study vaccine administrators) at the participating VTEU site. To preserve blinding and mask the color of study product in the syringe, the unblinded site research pharmacist will place a blinding tape or overlay on the syringe to mask its content. The vaccine will then be sent to an unblinded study vaccine administrator for administration to the subject.

The unblinded study vaccine administrator is a study personnel member credentialed to administer vaccines and may also participate in dose preparation, but will not be involved in study-related assessments or have subject contact for data collection following study vaccine administration.

The Safety Monitoring Committee (SMC) may receive data in aggregate and presented by treatment arm. The SMC may also be provided with expected and observed rates of the expected AEs in an unblinded fashion, and may request the treatment arm be unblinded for an individual subject if required for safety assessment. The SMC will review grouped and unblinded data in the closed session only. Refer to the protocol-specific Manual of Procedures (MOP) for unblinding procedures.

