5.4.5. Handling of Withdrawals

The primary reason for withdrawal from this trial will be recorded on the Study Status data collection form. Subjects will be encouraged to complete the Early Termination Visit. The Early Termination Visit procedures are listed in [Section 7.5](#).

Subjects who withdraw, or are withdrawn or terminated from this trial, or are lost to follow-up after signing the ICF, randomization, and receipt of study vaccine may be replaced to ensure each vaccine arm has at least 20 evaluable subjects, up to a total of 60 evaluable subjects. In order to be evaluable, a subject must receive the ChAd3-EBO-Z vaccine at Visit 1 and the booster vaccination of either ChAd3-EBO-Z, MVA-BN®-Filo, or placebo on Day 8 as determined by randomization.

Subjects who withdraw, or are withdrawn or terminated from this trial, or are lost to follow-up after signing the ICF and randomization but before receipt of study vaccine may be replaced.

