11.4.5. Missing Values and Outliers

All attempts will be made to collect all data per protocol.

As missing data are expected to be minimal, no imputation will be performed for missing values. Any data point that appears to be erroneous or inexplicable based on clinical judgment will be investigated as a possible outlier. If data points are identified as outliers, sensitivity analyses will be performed to examine the impact of including or excluding the outliers. Any substantive differences in these analyses will be reported.

For the transcriptomics endpoint, extreme data points will be identified by inspecting global patterns in the data. Experimental meta-data will be examined to see whether the outlying pattern can be attributed to experimental error such as sample mislabeling. Excluded outliers will be documented in the CSR. Due to the complexity, no sensitivity analysis will be carried out for the transcriptomics endpoints.

Please see the separate document **“Statistical Analysis Plan”** for additional information.

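### The RNA-Seq plan provides a batch term when batch is unrelated to study group, but no adjustment when batch is partly associated with group, the case that biases the between-group contrasts

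*Protocol*

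**What the plan says.** Protocol 11.4.4 (Exploratory Data Analyses) fits edgeR negative binomial models to find genes that change from pre-vaccination within each group, "as well as genes that were DE between study groups". On batch it says: "Principal component analysis, non-metric multidimensional scaling, and hierarchical clustering analysis will be used to identify potential global outliers and systematic batch effect". Then: "If the analysis reveals a systematic batch effect that is not associated with study group, it will be accounted for by adding a batch"; the term is a blocking factor in those models. It gives no criterion for judging association and no rule for a batch effect that is associated with group, whether partly or completely.

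The declaration rule is: "Genes with a FDR-value < 0.05 and a fold change of greater or equal to 1.5-fold (up or down regulation) will be deemed" significant. The section allows the fold cut-off to be revised in the light of the observed effects. Protocol 11.4.5 adds: "Due to the complexity, no sensitivity analysis will be carried out for the transcriptomics endpoints".

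On layout, allocation is 1:1:1 (Protocol 5.4.1), and Protocol 5.4.2 says: "Laboratory personnel performing experimental assays including antibody assays will also be masked to subject ID and study visit". No supplied section balances sequencing batches over groups or keeps a subject's samples together. The supplied SAP does not mention batch. Its Preface and sections 4.5.3, 6.8 and 10 refer the systems-biology endpoints to an addendum that is not among the documents.

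**The concern.** For a contrast between arms, a batch effect spread evenly over the arms costs precision but causes no bias. A batch effect that falls unevenly on the arms shifts the contrast. If the overlap is only partial, a blocking factor removes that shift. The written condition grants the factor in the first situation and is silent on the second.

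An analyst who follows the sentence literally could omit the term where it is needed. Genes could then be called differentially expressed between boosts because of processing, and would pass into the clustering and pathway enrichment. Benjamini-Hochberg adjustment handles multiplicity and presumes valid p-values. It does not remove a bias common to many genes. No transcriptomics sensitivity analysis is planned that might expose the problem.

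**Working it through.** The documents give no error rate, batch count or batch size for this analysis, so there is no planned figure to reproduce. Everything about batches below is an assumption.

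**Inputs from the documents.** Protocol 5.4.5 sets "at least 20 evaluable subjects, up to a total of 60 evaluable subjects", so a pair of arms is 20 v 20. Protocol 11.4.4 pools the groups before the second vaccination. Protocol 3.2.3 lists RNA-Seq on Days 2, 3, 4, 6, 8, 9 and 15, and the Day 8 blood is drawn before the boost. The between-group contrasts therefore fall on Days 9 and 15, two of the seven post-baseline days.

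**Assumptions.** Two batches; mirror-image splits a/(20−a) v (20−a)/a; one visit; no true group effect.

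**Step 1, bias and cost.** Let Δ be the difference between arms in the share of samples in batch 1, and β the batch effect on the log scale.
- Bias of the unadjusted contrast = Δ × β.
- Variance inflation with the batch term = 1/(1 − Δ²).
- Batch fold change that creates a spurious 1.5-fold group difference = 1.5^(1/Δ).

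| Split | Δ | Variance inflation | Batch fold giving a false 1.5-fold |
|---|---|---|---|
| 12/8 | 0.2 | 1/(1 − 0.04) = 1.04 | 1.5^5 = 7.59 |
| 15/5 | 0.5 | 1/(1 − 0.25) = 1.33 | 1.5^2 = 2.25 |
| 18/2 | 0.8 | 1/(1 − 0.64) = 2.78 | 1.5^1.25 = 1.66 |
| 20/0 | 1 | not estimable (rank 2 for 3 columns) | 1.5 |

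**Step 2, per-gene type I error at nominal 5%** (simulation, unit-variance normal errors).

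| Split | Shift 0.5 SD | 1 SD | 1.5 SD | With batch term |
|---|---|---|---|---|
| 10/10 | 4.3% | 3.1% | not run | 4.8-5.4% |
| 13/7 | 7% | 10% | 15% | about 5% |
| 15/5 | 11% | 27% | 48% | about 5% |
| 18/2 | 23.0% | 65.2% | not run | about 5% |

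Repeat runs of the 15/5, 1 SD cell gave 27% to 28%. At 10/10 there is no bias, so adjustment there serves precision only.

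**Step 3, negative binomial check** at 15/5 (assumed mean 100, dispersion 0.1; 500 runs). A 2-fold batch effect gives a false group fold change of 0.71 and rejection in 70.8% of runs unadjusted, against 1.00 and 7.4% adjusted. A 1.5-fold batch effect gives 39.0% against 7.4%.

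**Step 4, the plan's own rule.** Declaration needs FDR < 0.05 and at least 1.5-fold, which is log2(1.5) = 0.585. At 15/5 the spurious shift is 0.5 × (shift in SD) × (log2 SD). For a 1 SD shift and log2 SD of 0.3 to 1.0 it is 0.15 to 0.50. For 1.5 SD it is 0.225 to 0.75. With 40,000 independent null genes, the share falsely declared is about 0% at 0.5 SD, 0-1.4% at 1 SD and 0.01-22% at 1.5 SD. The width of each range reflects the assumed SD.

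**Step 5, how likely such a split is by chance.** For two arms of 20 and two batches of 20, the two-sided hypergeometric probability of 15/5 or worse is about 0.4%, and of 13/7 or worse about 11%. With 60 samples in two batches of 30, at least one of the three pairs of arms is as uneven as 13 v 7 in about 19% of layouts.

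**The case against.** Several points on the other side stand.

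- **The text says if, not only if.** A reader might infer that confounded contrasts will be run and reported unadjusted. The protocol never says so. That is an inference from silence, and the addendum could fill the gap without contradicting 11.4.4.
- **A reader might also infer that the rule is backwards throughout.** It is not. For the within-group comparisons with pre-vaccination, the harmful confounder is batch with visit. A visit-related batch effect not associated with group meets the stated condition and gets the blocking factor.
- **The condition has a plausible purpose.** When batch and group are completely aliased, no blocking factor can help. As worded, though, the condition also covers partial association, where it can.
- **Headline per-gene rates overstate the effect under this plan.** The FDR and fold rule cuts them sharply (step 4). It is not claimed that genes will be falsely declared, only that they can be. The cut-off may also be revised.
- **Randomisation and masking make strong imbalance unlikely.** Averaged over layouts independent of arm, unadjusted type I error is 4.8-5.2%. This reassures only in part. All genes share the one layout used, so an uneven layout affects them together, and masking does not guarantee a random layout.
- **Bias largely cancels** if each subject's samples share a batch and arms are compared on change from Day 1. The outcome in Protocol 3.2.3 is change from Day 1, but no supplied section specifies the batch layout. Specimen handling is left to the Manual of Procedures, which was not supplied.

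**Conclusion.** The gap is real but narrow. Protocol 11.4.4 provides a batch term when batch is unrelated to study group and no adjustment when it is partly related, although that is where the Day 9 and Day 15 group contrasts are biased and the term is still estimable. No supplied section closes the gap; the SAP addendum may.

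The size depends on the assumed shift and split. At 15/5 it runs from nothing declared falsely to about a fifth of null genes under the plan's rule, and a split that uneven is rare under random layout. Milder imbalance is common enough to plan for.

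The documents do not show that a confounded batch effect exists, or that one would knowingly be left in. Protocol 11.1 describes the systems-biology work as hypothesis-generating, and no primary or secondary result depends on it. The case for changing the sentence is that the remedy is standard and cheap.

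**What to change.** Replace the batch sentence in Protocol 11.4.4, and carry the same text into the SAP addendum:

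> Any detected batch effect will be included as a blocking factor in the negative binomial models whenever it is estimable together with study group and visit; contrasts for which batch is completely aliased with study group or visit will be flagged as not interpretable.

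This also removes the need to define when batch counts as associated with group.

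The cost is one sentence, the degrees of freedom for batch, and the variance inflation of step 1 when batch and arm are correlated: small at 12/8, material at 18/2.

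Optional and secondary, if sequencing has not been done: the data coordinating center, which holds the randomisation code, could supply a layout that keeps each subject's samples in one batch and balances arms over batches. It needs an unblinded party, because assay staff are masked to subject and visit and coded identifiers do not reveal the arm.
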